### 7.0 Data and Specimen Banking

- 7.1 N/A
- 7.2 N/A
- 7.3 N/A

### 8.0 Sharing of Results with Subjects

8.1 After completion of analyses, overall study results will be shared with participants in the form of a lay summary and/or infographic. This information will be sent to participants via the email they consented to using for study purposes.

> Any manuscripts for academic publication or other publicly available materials generated as a result of this work will not individually identify participants in this study.

## 9.0 Study Timelines

9.1 Participants in the TT-C arm will be asked to complete the intervention within one month. They will also be asked to complete follow-up surveys up to 3-months post-baseline. Participants in the SOC arm will also be asked to complete study activities up to 3-months post-baseline. Of note, those in the SOC arm who decide to access the TT-C app after the 3-month follow-up survey will be asked to complete additional surveys at 4- and 6-months post-baseline.

Recruitment of subjects is expected to be completed within 9 months of study launch. Primary outcome analyses are expected to be completed with 6 months of end of data collection.

# 10.0 Inclusion and Exclusion Criteria

10.1 All potential participants (whether recruited online or in-person) will complete an online screening survey via Qualtrics and REDCap to obtain consent to be screened and verify all inclusion criteria. Screening may occur on the same day as enrollment or beforehand. The online screening survey will begin with a script that will be read by participants to explain the purpose of screening and clarify that if they are eligible, they will be invited to participate in the study. The script will also provide general information about the research study, the nature of the screening questions and related potential risks, the approximate length of the screening (~5 minutes), the confidentiality of the screening information, the use of any screening information obtained, the ability to skip any questions or withdraw at any time and contact information of key study personnel. After reading this screening script, participants will be asked if they are interested in participating and agree to voluntarily complete the screening procedure. Participants will electronically indicate their agreement and then take the survey.

Those who meet eligibility criteria will be asked to record the first name, e-mail, and phone number if interested in participating; those disinterested in participating can decline by exiting the website. Potential participants who do not meet eligibility criteria will be asked if they would like to be contacted about other research studies and, if so, to provide contact information.

- 10.2 Inclusion Criteria:
  - Ages 18-29, inclusive

- Identify as African American/Black
- Able to speak and read English
- Has access to personal smartphone
- Current resident of AL, GA, NC

Exclusion Criteria:

- Aged younger than 18 years or older than 29 years
- Does not identify as African American/Black
- Non-English speaking
- Does not live in AL, GA, NC
- Unable to provide informed consent
- Receipt of full COVID vaccine series (including vaccination and booster or prior participation in a vaccine trial)

#### 10.3 Special populations:

- This study will not include adults unable to consent
- This study will not include individuals who are not yet adults (infants, children, teenagers)
- This study *may* include pregnant people as they are not specifically excluded. Their status as pregnant should not affect their ability to complete any of the outlined study activities, nor should the outlined study activities affect their pregnancy
- This study will not include prisoners

### **11.0 Vulnerable Populations**

11.1 NICHD has concluded that this protocol does NOT meet Federal requirements governing prisoner participation in human subject research and should NOT be considered by local IRBs for the recruitment of prisoners. Subjects enrolled who subsequently become incarcerated or are placed in detention may not continue study participation. Study visits cannot be conducted during the period of incarceration or detention

### 12.0 Local Number of Subjects

12.1 N/A

12.2 N/A

### 13.0 Recruitment Methods

13.1 Our recruitment strategy includes: 1) free and paid advertising and posting on social media sites; 2) advertising through targeted patient recruitment companies; 3) distribution through national organizations working with AA-YA, including HBCUs; and 4)

distribution through our community partners and other network collaborations.

- 13.2 Participants will be sourced from 1) social media sites; 2) targeted recruitment companies; 3) distribution through national organizations working with AA-YA, including HBCUs; and 4) our community partners and other network collaborations in AL, GA, NC.
- 13.3 We will use methods successfully deployed in our prior studies to recruit through social media sites frequented by AA-YA and rely on our strong network of community and academic partners for additional dissemination. Recruitment procedures may vary slightly depending on the community organization and study phase, which will be negotiated prior to the beginning of each phase of the study. For the focus groups and RCT, we will also follow respondentdriven sampling (RDS) methods and use a long-chain referral method to supplement recruitment.
- 13.4 We will use text and photos in combination for the Tough Talks COVID research study recruitment campaign. One or more text elements will be combined with photos to create engaging advertisements. The language, photos and graphics might be used alone or with text statements on a variety of online platforms including but not limited to, websites, social media, online news outlets, mobile phone apps, social networking sites, micro-blogging outlets, photo sharing portals, etc. The language and images may also be used for printed materials, including but not limited to buttons, stickers, palm cards, flyers, and print advertisements. All ads will identify Tough Talks COVID as a research study. A detailed recruitment plan providing example advertising text and images is appended to the IRB submission.
- 13.5 TT-C arm participants are compensated (using an e-gift card) for completion of baseline (\$50), 1-month (\$50), and 3-month surveys (\$50), \$50 for completing 75% of the app activities, and \$50 for exit interviews (up to \$250 in total). These participants will also be given the opportunity to complete an optional module of questions about Monkeypox as part of the baseline survey for an additional \$10. In total, TT-C arm participants could be compensated up to \$260.

SOC arm participants are compensated (using an e-gift card) for completion of baseline (\$50), 1-month (\$50), and 3-month surveys (\$50) (up to \$150 in total). These participants will also be given the opportunity to complete an optional module of questions about Monkeypox as part of the baseline survey for an additional \$10. If an SOC arm participant decides to engage with the TT-C app when offered after the 3-month follow-up, they could complete an

additional survey at 4- and 6-months post-baseline, for \$50 each, and \$50 for exit interviews. These participants will also receive a \$50 completion incentive if they complete at least 75% of the app activities. In total, SOC arm participants could be compensated up to \$360.

13.6 N/A

## 14.0 Withdrawal of Subjects

14.1 The principal investigator has the authority to withdraw any participant at any time if in their opinion it would be in the best interest of the participant. The participant will be informed of this withdrawal and explained the rationale. Withdrawal will be documented in the study tracking system.

Subjects will be prematurely discontinued from the study if any of the following occurs:

- a. The subject withdraws consent/assent
- b. The study is cancelled by the NIH (or other administrative entity)
- c. The study is cancelled for other administrative reasons

d. Death of the subject

- 14.2 Participants may end their participation in the study at any time. No further data collection will occur from the date the decision is made to permanently discontinue the subject from the study. Participants who experience distress during the study while at the community partner organization will be offered counseling on site. Participants who experience distress during the study and do not come to the partner organization for a visit will be provided a list of community referrals via phone or e-mail. Any unexpected adverse events that meet the unanticipated problem (UP) reporting criteria will be immediately reported to the IRB of record and the respective sites' IRBs if applicable. A Study Stop Form will be completed at this time.
- *14.3* No further data collection will occur from the date the decision is made to permanently discontinue the subject from the study.

# 15.0 Risks to Subjects

15.1 We identified the following as possible risks to subjects and describe below how we plan to address those risks:

Breach of Confidentiality: A potential risk to participants is violation of confidentiality. We will take the utmost caution to protect the confidentiality of all responses. We will minimize this risk by maintaining confidentiality and discretion throughout all aims of the

> study. Files – audio, paper and electronic- will not have any identifying information about the study participants and will be tracked through a unique SID and participant code. All audio recordings will be downloaded and stored on a password-protected, encrypted computer in locked offices at FSU and subsequently transferred to FSU encrypted servers. Transcription of audio files will be conducted using a HIPAA-compliant transcription service. Any names mentioned in the audio files will be redacted during transcription. Interview transcripts will be kept on FSU secure servers. Analysis of transcripts will be conducted on a passwordprotected, encrypted computer. Hard copies will be kept in locked files. We will take every available step to minimize the risk of identifying/linking data being subpoenaed, stolen, or inadvertently released. First, the Tough Talks-COVID study team has acquired a Certificate of Confidentiality from the NIH. Second, the study will safeguard against the risk of the linking information being stolen by keeping such information in a locked Excel spreadsheet on a secure server at FSU to which only essential study personnel who have completed CITI certification for human subjects research ethics training (http://citiprogram.org) will have access. We have also included numerous features to ensure app security and privacy. All relevant app communications (e.g. those between participants or those between participants and staff) will be secured via industry standard encrypted SSL communications links. These connections will ensure that all communications are inaccessible to unauthorized third parties. Furthermore, the app can be updated regularly to address any unforeseen security updates to the software libraries underlying the secured communication links. Beyond encrypting communication, users will need to log in with a username and password to access the app, even if the use of their phone is "unlocked." This will allow the user to share their phone generally with others without granting access to TT-C app. These software security solutions will provide the layers of both communications security and physical access security to ensure that only authorized users have access to the information stored on the phone as well as the information being shared over communications links. We will take special care to ensure that TT-C addresses participant privacy. During app onboarding, study staff will assist youth in choosing a discreet and anonymous username. Moreover, mobile phone screens themselves are also constructed to prevent surreptitious observation.

> Emotional discomfort: It is possible that the study may precipitate discomfort and/or an emotional response when AA-YA answer questions about potentially sensitive topics such as medical mistrust. Further, participants may feel embarrassed about discussing sensitive issues. All participants will be told during the informed consent

> process that their participation is voluntary and that they can chose to stop participating at any time without any consequences. Based on our experiences using similar data collection methods with youth in past studies, the likelihood and seriousness of this risk is minimal and we will strive to create a safe and comfortable environment for all study participants.

All sites have specific policies governing the treatment of human subjects. These policies specify that medical and psychological assistance will be available in the immediate environment in the event a participant should experience any adverse reactions resulting from study procedures.

While participants will be informed that they may refuse to answer any question at any time, responses or reactions to certain questions may indicate distress on the part of the participants. If at any time during the study, a participant divulges that he or she is at risk for harm, including but not limited to being abused or experiencing violence, if harm is suspected or likely, or if the participant states he or she is suicidal/homicidal, measures will be taken to ensure his or her safety. Reporting will be done as appropriate to the situation and the legal statutes, including reporting to child protection agencies or other appropriate agencies and referrals will be provided to appropriate support, counseling, or treatment resources.

- 15.2 N/A
- 15.3 N/A
- 15.4 N/A
- 15.5 N/A
- 15.6 N/A

### **16.0** Potential Benefits to Subjects

- 16.1 The risk to individual participants is small and the potential benefit to both the individual and society is substantial. The main benefit of the proposed study to society is the development of a potentially feasible and acceptable mobile app that promotes autonomy and improves COVID-19 vaccine uptake amongst AA YA and their social networks. This study is poised to reduce COVID morbidity and mortality among AA YA and their social networks, including peers and older adults. Therefore, the risk/benefit ratio is favorable.
- *16.2* Participation in this study may result in no direct benefit to participants.

### 17.0 Data Management and Confidentiality

17.1 Sample Size Considerations: Sample size calculations were conducted using simulation methods. The simulations: a) Step One: specify probabilities of vaccination and sample sizes for the three treatment groups and draw random samples of the specified sizes from binomial distributions with the specified probabilities treated as binomial parameters; b) Step Two: compare the outcome rates in the three samples using logistic regression and record whether the 2 degree-of-freedom test for differences is statistically significant; c) Step Three: make pairwise comparisons treatment arms using logistic regression; and d) Step Four: Repeat process 1,000 times and calculate power as the proportion of data sets (of 1000) generating statistically significant results.

Power calculations were conducted assuming that dropout would be equivalent across arms, and that approximately 15% would be loss to follow-up; therefore, assuming 250 306 participants will complete the primary endpoint assessment (125 153 per arm). Exhibit 1 depicts graphically the estimated detectable effect sizes (as a difference in proportion receiving any COVID vaccine) we will have 80% power to detect given a sample size of 250306, range of control arm rates of vaccine uptake, and assuming two-sided  $\alpha$ =0.05. If the rate of COVID vaccination in the control arm is between 10-20%, we will have 80% power to detect a difference in vaccination of 1312-146% between arms. If the rate of vaccination in the control arm is higher (30%), we will have 80% power to detect a 1715.5% difference in vaccination rate between arms. The detectable effect size is lowest highest when the control proportion is closer to 50%, but we will still have 80% power to detect a difference of 17.616% if the rate of vaccination in the controls is 50%. We anticipate vaccination rate in the control arm will be low given that vaccines have been available for some time. Therefore, we expect a total sample size of 300 360 will provide sufficient power to detect a clinically meaningful difference in vaccine uptake.

**Exhibit 1.** Estimated detectable effect size with an effective sample size of 306 (153 per arm) and range of possible vaccination rates in the control arm; 80% power and two-sided alpha of 0.05.

Effectiveness Outcomes: Primary effectiveness outcomes are COVID vaccine uptake and completion of series; secondary effectiveness outcomes are VH, confidence, and knowledge, attitudes, and beliefs. We will also collect implementation outcomes, SCT constructs targeted by TT-C, COVID-specific risks and behaviors and pertinent constructs that have been validated in the extant literature on AA-YA (Table 5).

Analyses of Effectiveness Data: We will use logistic regression to determine the effect of treatment arm on the probability of vaccination uptake (yes/no) and COVID vaccine series completion (yes/no) at month three. We will determine whether the overall 2degree-of-freedom test for differences among treatments is statistically significant. If so, we will examine the parameter estimates and standard errors to determine where difference lie between the three arms. We will focus on the odds ratios for comparing the probability of infection in each of the two treatment groups with the probability in the controls. The secondary outcomes of VH, vaccine confidence and vaccine knowledge, attitudes and beliefs will all be assessed using previously validated scale scores, each of which will consist of the continuous sum of responses to a series of questions with Likert scale responses. We will use linear regression models with treatment group as the exposure to determine whether secondary outcomes vary among treatment groups. Lastly, we use the causal mediation framework proposed by Valeri and Vanderweele to understand mechanisms for any intervention effects through each of our hypothesized mediators. We will use the gformula command in Stata which uses the mediational g-formula to estimate the controlled direct, natural direct, and natural mediated (indirect) effects.59

Implementation Outcomes and Analysis: We will conduct qualitative interviews with a group of purposively selected AA-YA participants (est. n=12-16) and site staff (est. n=6-8) to assess barriers and facilitators to TT-C intervention implementation. We will conduct 12-16 in-depth exit interviews (~4-6 per state) on a rolling basis after participants have concluded the 3-month study cycle. All interviews will be audio-recorded and transcribed verbatim. Qualitative analyses will be conducted in the NVivo coding program. From AA-YA, we will ask questions on how sociocultural non-intervention contexts affected the likelihood of vaccine acceptance, vaccine series completion, and VH. From staff, we will collect qualitative data on

the inner and outer contexts affecting implementation with ongoing fidelity such as on policies, environment, funding, and social conditions that could influence intervention scale-up and sustainment. Due to the urgency of addressing COVID VH, we will use Rapid Content Analysis that is routinely leveraged in implementation science to assess and disseminate results quickly and accurately. Findings will be explored as a function of participant age, sex, state, and setting. Qualitative findings will provide a direct line into real-world implementation considerations.

Note: Any deviations from the analysis plans outlined above or in the sections that follow will be documented and justified in the Statistical Analysis Plan developed for this protocol.

Qualitative Data Analysis: FSU will use NVivo software to perform all qualitative analyses. NVivo is a web-based application for organizing and analyzing textual, audio, and video data (qualitative) along with outstanding functionality for their integration with survey, test score, ratings, and demographic data (quantitative). NVivo employs the highest levels of data encryption available for a web application in all data storage, back up, and transmission. NVivo allows for project specific encryption feature.

Missing Data: In sensitivity analyses, we will also use inverse probability of treatment weights (IPTW) to account for missing data and potential differential retention between study arms over the study period. We will weight outcome models using stabilized inverse probability-of-censoring weights that include treatment arm as a predictor to account for differential loss to follow up. Pooled logistic regression models will be used to estimate the numerator and denominator of censoring weights, and weights will be multiplied over time. The denominator will be calculated using a logistic regression model for loss to follow up, including treatment arm. Weights will be stabilized to reduce potential bias from extreme weights. Numerator weights for the stabilized IPTW will be estimated using a logistic regression model for loss to follow up without covariates. Distributions will be examined to ensure weights have a mean of 1; extreme weights that may introduce bias will be trimmed by cutting the top or bottom 1%. Analogous weight will be calculated for missing data, including relevant covariates, and will be multiplied by censoring weights.

Several procedures will be used to conduct data analysis when data for either outcomes or covariates are missing. The first step will be to assess the extent and pattern of missing data. If data are missing for only a few cases, then data analysis will be conducted only on study participants with complete data. However, when such a

> strategy would result in loss of data from a substantial proportion of participants, or if this approach would lead to biased or inaccurate results, then some form of imputation will be performed. The form of imputation used will depend on the nature of the data that are missing. For example, data that are collected repeatedly might be imputed using the "last value carried forward" method; and in some instances, interpolation between neighboring points might also be used.

When the primary endpoint is missing, one data analysis will be conducted using only cases with the endpoint. Subsequent analysis will be done where missing endpoints are imputed. Hot-deck imputation or regression imputation may also be used in this context.

17.2 We will monitor recruitment and retention rates, site compliance with study procedures, and provide technical assistance for queries and concerns. Encrypted data will be saved on an FSU server, with password protection. We will examine data quality weekly (e.g., missing data, assessment of distributional assumptions, identification of outliers) and before statistical analysis is conducted. Comparability between participants across all three arms will be reviewed. Missing scale data will not be estimated. Comparability between sites and states will be examined. Data will be aggregated for general analysis purposes; however, if significant differences emerge, separate analyses comparing outcomes between sites or states detailing differences will be conducted.

Investigators receiving federal funding must adhere to the Code of Federal Regulations (CFR) to protect research participants and produce reliable study information. Sites participating in research sponsored by the NICHD need to have an internal quality assurance (QA) plan that will identify problems and correct errors in research study records.

Site monitors may visit participating study sites to review a selected portion of the individual participant records, including assent/consent forms, CRFs and supporting source documentation to ensure the protection of study subjects, compliance with the protocol, and accuracy and completeness of records. Regulatory files, as required, will also be inspected to ensure that regulatory requirements are being followed.

The site investigator will make study documents (e.g., consent forms, case report forms) and pertinent hospital or clinic records readily available for inspection by the local IRB, the site monitors, the NICHD, the Office of Human Research Protection (OHRP), or the sponsor's designee for confirmation of the study data.

- 17.3 We will take every available step to minimize the risk of identifying/linking data being subpoenaed, stolen, or inadvertently released. First, per Section 2012 of the 21st Century Cures Act as implemented in the 2017 NIH Certificates of Confidentiality Policy, all ongoing or new research funded by NIH as of December 13, 2016 that is collecting or using identifiable, sensitive information is automatically issued a CoC. As noted on the NIH website (http://grants.nih.gov/grants/policy/COC/faqs.htm#187), a Certificate of Confidentiality will help the research team "...avoid compelled 'involuntary disclosure' (e.g., subpoenas) of names and other identifying information about any individual who participates as a research participant (i.e., about whom the investigator maintains identifying information) during any time the Certificate is in effect." We have applied for and received Certificates of Confidentiality for other NIH-funded research projects, and given the sensitive nature of the data collected for this project, do not foresee difficulty securing one for this study. Second, all research staff members are required to complete ethical clearance certification regarding protection of human's subjects through their relevant IRBs. Third, all studies will have documented procedures to safeguard against the risk of the linking information being stolen by keeping such information in locked spaces to which only essential study personnel who have completed CITI certification for human subjects research ethics training (http://citiprogram.org) will have access.
- 17.4 N/A

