### 4.0 Study Endpoints

- 4.1 The primary study endpoint is COVID vaccine uptake and series completion. The secondary study endpoint is change in vaccine hesitancy, vaccine confidence, and change in knowledge, attitudes, and beliefs.
- 4.2 N/A

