### 6.0 **Procedures Involved**

6.1 This study will consist of three distinct aims to develop and test the TT-C intervention for COVID vaccine hesitant AA-YA. Aims 2 and 3 procedures are premised on the formative data collected in Aim 1.

Aim 3: Conduct a hybrid type 1 effectiveness implementation 2-arm randomized controlled trial with 360 AA-YA from AL, NC, and GA.

6.2 Enrollment: After screening eligible and agreeing to be contacted, eligible responses will be reviewed individually by study staff to determine authenticity and legitimacy. In addition to eligibility criteria, staff will review bot detection values as well as location based on IP address & latitude/longitude. If determined eligible, staff complete the Verification CRF and REDCap will email the individual with a unique consent form link to complete. Once completed, REDCap will send the baseline survey linked to their unique ID in REDCap.

After the baseline survey is complete, study staff will randomize the participant with the Randomization CRF to either the intervention or control group. Based on the study arm, study staff will either email the participant with the developed SOC materials or email the participant with a unique link to create their account for the TT-C app. If SOC, the participant will be compensated at this time.

If participant is randomized to intervention arm, they will be prompted to create their account with the provided link, then will be

> directed to download and login to the TT-C app. Once account creation is confirmed in the administrator portal, study staff will compensate the participant for enrolling.

Randomization: RCT participants will be randomized via block randomization into the control condition and TT-C (remote), each with a balanced 180 participants. Assignment will be stratified by state to achieve balance between intervention and control participants within a given study state.

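### The primary logistic models name treatment arm only; pre-specifying state and the baseline hesitancy score would be expected to add about 0 to 6 points of power for uptake

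*Combined protocol and SAP*

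**What the plan says.** Section 17.1 (Analyses of Effectiveness Data) states: "We will use logistic regression to determine the effect of treatment arm on the probability of vaccination uptake (yes/no". The same sentence covers series completion, both at month three. No baseline covariate or stratum term is named. The power simulation in 17.1 is also unadjusted, and its effect is expressed "as a difference in proportion receiving any COVID vaccine".

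Section 6.2 states: "Assignment will be stratified by state to achieve balance between intervention and control participants within a given study state". The revision history shows that this balancing by state was added in January 2023. Section 17.2 pools the data and calls for separate site or state analyses only where significant differences appear.

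Section 4.1 states: "The secondary study endpoint is change in vaccine hesitancy, vaccine confidence, and change in knowledge, attitudes, and beliefs". A change endpoint needs a baseline value, and 6.2 places the baseline survey before randomisation. The contents of that survey are not itemised in the text available. Covariates are mentioned only under Missing Data in 17.1, for imputation and weighting, and none is listed there.

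**The concern.** The trial rests on the premise that hesitancy influences vaccination, so a pre-randomisation hesitancy score is the natural prognostic covariate for the primary outcome. State is a design factor with no counterpart in the analysis. Leaving a stratification factor out of the model makes the standard error slightly too large if the factor predicts outcome. Leaving out a prognostic score lets chance imbalance add avoidable noise to the estimate. The planned power is close to 80%, so a gain from data that the trial should already hold would be worth having. If no covariates are named in advance, any later adjustment is open to the criticism that it was chosen after seeing the data.

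**Working it through.** **Inputs from the documents.** Section 6.2: "randomized via block randomization into the control condition and TT-C (remote), each with a balanced 180 participants". Section 17.1: "approximately 15% would be loss to follow-up", so 360 × 0.85 = 306; "Estimated detectable effect size with an effective sample size of 306 (153 per arm"; "80% power and two-sided alpha of 0.05". The detectable differences in 17.1 print with superseded and current figures run together. I read the current ones as 12, 14, 15.5 and 16 points at control rates of 10, 20, 30 and 50%. Section 17.1 still refers to three groups and a 2-degree-of-freedom test. I use the two-arm comparison that 6.2 describes.

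**Step 1: reproduce the plan's figures.** With n = 153 per arm and p̄ the mean of the two rates, power = Φ{[Δ − 1.96·√(2p̄(1−p̄)/n)] / √[(p₀(1−p₀)+p₁(1−p₁))/n]}.

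For 20% vs 34%, p̄ = 0.27. The null standard error is √(2 × 0.27 × 0.73/153) = 0.0508. The alternative standard error is √[(0.16 + 0.2244)/153] = 0.0501. Power = Φ[(0.14 − 0.0995)/0.0501] = Φ(0.81) = 79.1%. The other stated pairs give 82.0% (10% vs 22%), 80.2% (30% vs 45.5%) and 81.3% (50% vs 66%). Solving for 80% power gives 11.6, 14.2, 15.5 and 15.8 points. The plan's figures therefore reproduce for an unadjusted test. The superseded figures reproduce at 125 per arm, which supports my reading of the edits.

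**Step 2: power after adjustment.** The documents give no R² or odds ratio linking baseline hesitancy to uptake, so its strength is assumed (odds ratio 1.0 to 2.5 per SD, direction immaterial). State effects are also assumed. The statewide vaccination rates in 3.3 (61.8, 64.3 and 82.2%) give a North Carolina to Alabama odds ratio of (0.822/0.178)/(0.618/0.382) = 2.85, used as the upper end. Marginal rates were held at the plan's values. There were 4,000 simulated trials per scenario, with Monte Carlo error of about 0.6 points on each power. Wald tests compared arm alone with arm, state and score.

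| Score OR per SD | State OR | 10% vs 22%: gain | 20% vs 34%: gain | 30% vs 45.5%: gain |
|---|---|---|---|---|
| 1.0 | 1.0 | 0.2 | 0.2 | −0.2 |
| 1.0 | 2.8 | 0.8 | 1.7 | 1.3 |
| 1.5 | 1.0 | 0.9 | 0.9 | 1.5 |
| 2.0 | 1.0 | 2.4 | 3.1 | 3.1 |
| 2.0 | 2.8 | 3.5 | 3.8 | 4.5 |
| 2.5 | 1.5 | 4.4 | 4.6 | 6.2 |

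Gains are in percentage points of power. A separate simulation (10,000 trials per scenario, 20% vs 34%, state effects from the 3.3 vaccination rates) agrees: 80.0 to 82.6% at an odds ratio of 0.67 per SD, 79.8 to 83.8% at 0.50, and 79.6 to 85.8% at 0.40.

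**Step 3: cross-check.** At 80% power the expected test statistic is 1.96 + 0.842 = 2.802. If the covariates explain a share R² of outcome variance, power ≈ Φ[2.802/√(1−R²) − 1.96]. This gives 82.0% at R² = 0.05, 83.2% at 0.08, 84.0% at 0.10 and 86.0% at 0.15. A gain of 3 to 6 points therefore corresponds to R² of about 0.08 to 0.15.

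**Step 4: validity.** With no effect (20% in both arms), rejection rates were 4.3 to 4.8% for arm only and 4.6 to 5.5% adjusted. The mean risk difference was about 14.0 points under both the unadjusted and the standardised estimator at 20% vs 34%.

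**Step 5: missing baseline scores.** With an assumed 10% of scores missing (20% vs 34%), a complete-case adjusted model had 78 to 79% power, against about 80% for arm only. Filling missing scores with the overall mean restored 82 to 83%.

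**The case against.** The strongest reply is that nothing is broken. The arm-only test controls type I error, its estimate is unbiased, and its confidence interval already allows for chance imbalance. A difference defined as detectable with 80% power will of course show about 80% power. All of that stands. A reader might infer that the trial is underpowered or that its primary analysis is invalid; the documents support neither.

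A reader might also infer that the plan certainly forfeits 3 to 6 points. That does not follow, because the prognostic strength of hesitancy is not given. The Study Summary limits Aim 3 to people who express hesitancy (10.2 omits this criterion), which may narrow the score and weaken it as a predictor. The state effect is uncertain too. The vaccination rates in 3.3 put North Carolina highest, while the booster rates in the same section (34.1, 34.9 and 25.1%) put it lowest. Neither set describes three-month uptake among trial participants. With the booster rates, state alone added about 0.1 to 0.4 points. At 10% vs 22%, with an odds ratio of 0.50 per SD and booster-based state effects, the total gain was about 2 points. Low control uptake is what 17.1 expects.

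Adjustment is also not free if scores are missing. Section 17.2 rules out filling in missing scale values, and 15.1 lets participants decline questions. As Step 5 shows, dropping those participants can cancel the gain. This stands, and the fix must deal with it.

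Finally, 17.1 does not forbid covariates; it names none. That narrows the criticism but does not answer it, since the power simulation is unadjusted and no covariate set is fixed anywhere.

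**Conclusion.** The point holds as one of efficiency and pre-specification. The primary models name only treatment arm, although a stratification factor and, by implication, a relevant baseline score are available. The unadjusted test meets its planned power. For uptake, adjustment would be expected to add about 0 to 6 points, and 3 to 6 only if hesitancy is a moderately strong predictor within this restricted population. State alone contributes about 0 to 2 points, so nearly all of a larger gain would come from the hesitancy score. If neither variable predicts uptake, essentially nothing is lost, provided that missing scores do not remove participants. These figures assume 153 completers per arm, the stated control rates and a baseline score measured before randomisation. Only uptake was simulated. Rates for series completion are not given, so no figure is claimed for it, although the same modelling argument applies.

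**What to change.** In 17.1 and the SAP, pre-specify the primary models for uptake and series completion as logistic regression on treatment arm, state (three levels) and continuous baseline hesitancy score. From each model, report the standardised risk difference with its confidence interval beside the odds ratio, which also matches the scale of the power statement. Keep the arm-only model as a supportive analysis.

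State that a missing baseline score is filled by a simple method that uses neither arm nor outcome, for example the overall mean, as an explicit exception to the rule on scale data in 17.2. No randomised participant with an outcome is then dropped. Confirm that the hesitancy scale is in the baseline survey.

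The cost is a few sentences and a little code; no new data are needed if the scale is already collected. At 10% vs 22% there would be about 153 × (0.10 + 0.22) = 49 events for four slopes, or about 12 per slope. The small downsides are that the adjusted odds ratio is conditional on the covariates, which the standardised risk difference addresses, and that one missing-covariate rule must be added.
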